#### **9.4.3 Loss to Follow-up**

For study purposes, patients will be considered lost to follow-up if any time-based assessment is missed and the corresponding data have not been received by the CC after making additional follow-up attempts using all contact methods available (eg, phone, fax, registered letter). At least 3 attempts will be made up to 4 months after the expected date of the missed assessment. The patient will be re-opened if additional information is later obtained. All HCPs and secondary contacts will also be contacted prior to considering a patient lost to follow-up. All data collected prior to the patient being lost to follow-up will be used for analyses, if possible. For analysis purposes, the date of study discontinuation will be recorded as the date of last contact.

Registry awareness, recruitment, and retention strategies to maximize enrollment and minimize loss to follow-up are described in [Section 9.4.4](#).

#### **9.4.4 Registry Awareness, Recruitment, and Retention**

##### **9.4.4.1 Registry Awareness**

The registry will utilize awareness strategies that have appeared to be effective in other pregnancy exposure registry programs. Increased awareness of the registry will use multiple approaches aimed towards both HCPs and patients, such as social media, paper and electronic media, and scientific conferences. The registry will also be included in labeling and listed on the FDA Office of Women's Health Pregnancy Registry website. Registry awareness activities and content will be evaluated on a regular basis to ensure target populations are being reached yet minimize any burden on the recipients. Channels for providing feedback on Registry material and corresponding with potential HCPs and patients will be detailed in a Recruitment and Retention Plan.

##### **9.4.4.2 Registry Recruitment**

Active outreach will occur to obtain reports of women with migraine who are exposed to erenumab-aooe during pregnancy, as well as women with migraine who may be eligible for the internal comparator cohort who receive medical care from the same clinical sites. Outreach efforts may include the following:

- Discussion of the Registry with Investigators participating in erenumab-aooe clinical studies, with periodic written reminders
- Collaboration with Investigators of independent migraine registries
- Notification of the Registry to neurologists and other practitioners who may prescribe erenumab-aooe, as well as migraine education and support groups, via the following:
  - Investigator awareness electronic flyer
  - HCP introduction letters
- Collection of patient referral information at enrollment (eg, HCP, website/internet, sponsor, etc.)

Recruitment of patients is dependent on several factors. Uptake of new medications such as erenumab-aooe is unpredictable and has the potential to impact the feasibility of meeting the recruitment targets in the U.S. In addition, the expected pace of exposure to pregnant women and the willingness of pregnant women to voluntarily participate in a registry are both difficult to predict. Continuous monitoring of patient recruitment rates (comparing projections with observed rates) will allow for strategies to be employed in response to any recruitment challenges.

##### **9.4.4.3 Registry Retention**

Registry retention efforts may include general study eNewsletters to HCPs communications that could include: engagement emails, SMS/email/Call reminders, or

'thank you' messages for patients and/or HCPs (where relevant). The projected versus observed drop-out rates will be continuously monitored. Retention planning will be performed in advance as part of the Recruitment Risk Management with triggers for implementation of actions identified, as well as steps to take if the rate of patient completion decreases. Retention efforts for both HCPs and the patients will be documented in the Recruitment and Retention Plan. Steps to ensure recruitment and retention of patients in the Registry include actions for implementation at study start, in addition to actions that could be implemented as the study progresses and new enrollment information becomes available.

#### **9.4.5 Safety Data Collection**

All AEs and SAEs in the erenumab-aooe exposed cohort are required to be recorded in the eCRF during the observation period. HCPs will report AEs and SAEs occurring during pregnancy through the infant's first year of life to the CC, who will enter them in the eCRF. See [Section 11](#) for a full description of safety procedures.

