## 9. Research Methods

### 9.1 Study Design

The design of this pregnancy exposure registry is consistent with relevant guidelines and recommendations ([FDA, 2019](#); [European Medicines Agency, 2005](#); [Gliklich et al, 2014](#); [Andrews et al, 2008](#)). This prospective observational registry will collect primary data from pregnant women with migraine and their healthcare providers (HCPs) (eg, primary care physician [PCP], neurologist [indication specialist], obstetrician [OB], nurse midwife or pediatrician) from the U.S. (see [Study Design Schema](#)). The coordinating center (CC) is responsible for obtaining informed consent and all patient and HCP contacts during the study. Patients' data obtained via questionnaires administered to patients or their HCPs will be recorded on electronic case report forms (eCRFs) by the CC.

Women who have been exposed to erenumab-aooe during the 16 weeks prior to their last menstrual period (LMP) or at any time during pregnancy are eligible for the

erenumab-aooe-exposed study cohort. The 16-week exposure period prior to LMP accounts for the effective half-life of erenumab-aooe (28 days; AIMOVIG® Prescribing Information), with an additional buffer added. Inclusion of exposures prior to LMP is based on the half-life and standard of care dosing schedule of erenumab-aooe. Dosing and treatment duration of erenumab-aooe as part of this observational study is at the discretion of the HCP in accordance with local clinical practice and local labeling.

The internal comparator cohort (erenumab-aooe-unexposed) will consist of currently pregnant women with clinically confirmed migraine who were not exposed to any CGRP mAb during 5 half-lives prior to their LMP or at any time during pregnancy. Internal comparator cohort patients will be enrolled and follow the same study procedures for follow-up and data collection as the erenumab-aooe exposed cohort.

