**Infant Follow-up (estimated at 12, 26 and 52 weeks of age)**

- Reporter of information (eg, patient, PCP, OB, neurologist [indication specialist], nurse midwife, infant HCP, other)
- Feeding behavior (including breastfeeding)
- Weight
- Length
- Head circumference
- Postnatal growth and development (ie, social/emotional, language/communication, neurocognitive, movement/physical development milestones)
- Breastfeeding status
- Evidence of any new congenital malformations and growth alterations since last follow-up
- Vaccination information
- Patient and infant AEs and SAEs (including event, start date, ongoing or end date, seriousness, severity, relationship to erenumab-aooe, outcome, action taken)

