### **9.7.3 Analysis of Safety Outcomes**

Interim safety reporting will be conducted every year and will be aligned with the periodic benefit-risk evaluation report (PBRER) reporting schedule. All AE verbatim terms will be recorded and coded using the Medical Dictionary for Regulatory Activities version 21.1 or later. All AEs reported will be analyzed by preferred terms on overall and within erenumab-aooe exposed and internal comparator cohorts.

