### **11.1.2 Serious Adverse Events**

An SAE is any AE as defined above that meets at least 1 of the following serious criteria:

- is fatal
- is life threatening (places the patient at immediate risk of death)
- requires in-patient hospitalization or prolongation of existing hospitalization
- results in persistent or significant disability/incapacity
- is a congenital anomaly/birth defect
- is an “other medically important serious event” that does not meet any of the above criteria

Obstetric complications that fall into the above categories are defined as SAEs in this study and should be reported to the CC. Normal delivery and elective cesarean sections performed for non-medical reasons (ie, scheduling, personal preference) and their related hospitalizations will not be considered SAEs, unless, in the view of the reporting physician, the hospitalization was prolonged due to a complication.

A hospitalization meeting the regulatory definition for “serious” is any in-patient hospital admission that includes a minimum of an overnight stay in a healthcare facility.

“Other medically important serious events” refer to important medical events that may not be immediately life threatening or result in death or hospitalization but may jeopardize the patient or may require intervention to prevent 1 of the other outcomes listed in the definition above. Examples of such events could include allergic bronchospasm, convulsions, blood dyscrasias, drug-induced liver injury, events that necessitate an emergency room visit, outpatient surgery, or other events that require other urgent intervention.

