#### **11.2 Safety Collection, Recording and Submission to Amgen Requirements**

This study is collecting information from patients and HCPs prospectively from enrollment through the end of follow-up (ie, if the patient is lost to follow-up, consent is withdrawn, death (mother and/or infant), study termination, or the study ends [whichever comes first]). All safety events (AEs, product complaints, and other safety findings) considered to have occurred following patient exposure to erenumab-aooe will be collected from signing of ICF. The CC is responsible for ensuring that all safety events that they become aware of during study period, are recorded in the patient's appropriate study documentation. Those safety events which are considered serious must also be submitted as individual safety reports to Amgen Safety via the applicable Amgen Safety Reporting Form (paper or electronic form) within 1 business day of CC awareness. Non-serious AEs must be reported in an expeditious manner, not to exceed 15 calendars days of CC awareness. Non-serious AEs must be reported in an expeditious manner, not to exceed 15 calendars days of CC awareness. Safety events that are suspected to be related to any medicinal product where there is no exposure to erenumab-aooe should be reported to the local authority in line with the local country requirements.

See [Appendix C](#) for sample Safety Report Form(s), [Appendix D](#) for Additional Safety Reporting Information regarding the AE grading scale used in this study. The CC may be asked to provide additional information for any event submitted, which may include a discharge summary or extracts from the medical record. Information provided about the event must be consistent with information recorded in the study documentation where safety data may also be recorded.

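### The protocol contradicts itself on whether AEs are recorded for the comparator cohort, so the by-cohort AE tables could differ through collection alone

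*Protocol*

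**What the plan says.** Two sections govern safety collection, and both tie it to erenumab. Section 9.4.5 opens: "All AEs and SAEs in the erenumab-aooe exposed cohort are required to be recorded in the eCRF during the observation period". It then refers the reader to Section 11 for the full procedures. Section 11.2 says that the safety events "considered to have occurred following patient exposure to erenumab-aooe will be collected from signing of ICF". For events suspected to be related to a medicinal product, it adds that those "where there is no exposure to erenumab-aooe should be reported to the local authority in line with the local country requirements".

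Other parts of the protocol carry no such limit. Section 9.1 states: "Internal comparator cohort patients will be enrolled and follow the same study procedures for follow-up and data collection as the erenumab-aooe exposed cohort". The second sentence of 9.4.5, on entry into the eCRF, names no cohort: "HCPs will report AEs and SAEs occurring during pregnancy through the infant's first year of life to the CC, who will enter them in the". The baseline list in 9.2.7 and every contact list in 9.2.8 include AEs and SAEs. The infant follow-up entry, for example, reads "Patient and infant AEs and SAEs (including event, start date, ongoing or end date, seriousness, severity, relationship to erenumab-aooe, outcome, action taken". Appendix E and all five tables of Appendix F repeat the item.

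The analysis section then assumes data from both cohorts: "All AEs reported will be analyzed by preferred terms on overall and within erenumab-aooe exposed and internal comparator cohorts" (Section 9.7.3).

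**The concern.** A table of AE frequencies by cohort can be read only if events were sought and recorded in the same way in both cohorts. Here the explicit recording duty names one cohort, while the table shows two. A coordinating center that follows 9.4.5 and 11.2 to the letter would record exposed women's events as an obligation and could treat comparators' events as optional. The exposed column would then tend to be fuller even if erenumab had no effect on any event.

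This cannot be left to the analysis stage. It is a rule about data collection, and a comparator event that was never recorded cannot be recovered later. Nor does it wait for the final report, since 9.7.3 also sets yearly safety reporting.

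**Working it through.** The protocol gives no figure for AE frequency or completeness of recording, so there is no plan figure to reproduce on this point. The check is a comparison of the text, followed by a short illustration.

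**Step 1: what each place implies for a comparator woman's AE**

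- 9.4.5, first sentence: the eCRF duty is stated for the exposed cohort only.
- 9.4.5, second sentence: providers report and the coordinating center enters, with no cohort limit.
- 11.2: collection covers events after erenumab exposure. Suspected drug-related events without that exposure go to the local authority.
- 9.1: same follow-up and data collection as the exposed cohort.
- 9.2.7, 9.2.8, Appendices E and F: AEs and SAEs listed with no cohort limit.
- 9.7.3: tabulated by preferred term within the comparator cohort.

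The first sentence of 9.4.5 and Section 11.2 point one way and the rest points the other. Nothing in the protocol says which prevails.

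**Step 2: whether the unrestricted lists settle it**

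Not fully. The same lists also carry erenumab start and stop dates, dose and reason for discontinuation with no cohort limit, although these can apply only to exposed women. Silence about cohort in a list is therefore weak evidence that an item is required of comparators. Section 9.1 is the strongest statement for equal collection, and it conflicts directly with 9.4.5 and 11.2.

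**Step 3: what unequal recording would do to the table**

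Let both cohorts have the same true AE frequency, and let comparator recording be a fraction c as complete as exposed recording. Then

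apparent ratio (exposed to comparator) = 1 / c.

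- c = 0.8: 1 / 0.8 = 1.25
- c = 0.5: 1 / 0.5 = 2.0

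The values of c are assumptions. The protocol does not plan to compute this ratio; it is what a reader would see on setting the two columns side by side.

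**Step 4: whether the primary outcome depends on the AE field**

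It does not. Malformations are a separate data element during pregnancy, at delivery, at 12, 26 and 52 weeks and at early termination (9.2.8). They are assessed in both cohorts (9.3.2) and adjudicated by a committee blinded to exposure (9.3.2.1.1, 9.8.4). One side route remains. An event is an SAE if it "is a congenital anomaly/birth defect" (11.1.2). Events within the scope of 11.2 may prompt requests for a discharge summary or record extracts, and adjudication uses all available records. If SAE reporting were confined to exposed women, their cases might arrive with fuller records. Blinding protects classification, but it cannot correct unequal record depth.

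**The case against.** The strongest reply is that most of the protocol has comparator AEs collected, so 9.4.5 and 11.2 are loose drafting rather than a one-sided design. The title of 11.2 includes submission to the sponsor, and its deadlines (1 business day for serious events, 15 calendar days for others) concern that submission, which may reasonably depend on exposure. Section 11.2 also makes the coordinating center responsible for documenting all safety events it learns of. AEs are neither a primary nor a secondary outcome in Table 3, and 9.7.3 describes tabulation within cohorts, not a test.

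Much of this stands. The protocol does not clearly intend to record AEs in one cohort only; it contradicts itself, and the table affected is descriptive. The reply does not remove the conflict, though. The wording of 9.4.5 concerns eCRF recording, not submission, and 11.2 uses the word for collection. Columns for two cohorts invite comparison even without a test.

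A reader might also infer that malformations will be found more readily in exposed women, pushing the primary risk ratio above 1. The documents do not support that. Malformations have their own prompts at the same contacts in both cohorts, nothing routes referral to the committee through SAE forms, and the sentence in 9.4.2 on sponsor follow-up of SAEs has no cohort limit. Ratios such as 1 / 0.9 = 1.11 or 1 / 0.8 = 1.25 can be written down for malformations, but they rest wholly on assumed capture rates that nothing in the protocol suggests.

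**Conclusion.** The contradiction is real and should be resolved. If 9.4.5 and 11.2 are followed as written, comparator AEs may be under-recorded and the by-cohort AE tables could show an excess with erenumab that comes from collection alone. The size is unknown; the 1.25 to 2.0 range shows sensitivity to assumed completeness of 80% down to 50% and is not a forecast. The effect is on descriptive tables, not on a formal comparison. For the primary malformation outcome, fuller records for exposed cases are a possible secondary route at most, and no defect is shown. The sample size is unaffected.

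**What to change.** Reword 9.4.5 and 11.2 so that maternal and infant AEs and SAEs are recorded in the eCRF in both cohorts, with the same prompts and the same follow-up queries. State separately that only submission of safety reports to the sponsor depends on erenumab exposure.

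If equal recording is not wanted, remove the comparator AE tabulation from 9.7.3, align 9.1, the 9.2.7 and 9.2.8 lists and Appendices E and F with that choice, and state that AE data are not comparative.

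The first option is a change of wording, since Appendices E and F already carry the fields. Its cost is some added data entry for comparators.

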#### **9.5 Study Size**

The sample size was estimated to assess the prevalence of major congenital malformations in infants of women with migraine exposed to erenumab-aooe during pregnancy and associated risk ratio with the internal comparator. Estimated sample size results ranged from 465 to 4,776 in each treatment group (1:1 exposed vs. unexposed internal comparator) to detect risk ratios ranging from 3 to 1.5, respectively ([Table 4](#)). To adequately power an internal comparison of the proportion of major congenital malformation events in the erenumab-aooe exposed, and assuming a 15% drop-out rate and a live birth rate of 62% ([FDA, 2002](#)), 1421 erenumab-aooe exposed pregnant women with migraine would need to be enrolled to observe 749 live births. This sample size would provide 80% power to detect a risk ratio of 2.0 or greater in major congenital malformations relative to an assumed prevalence of 3% in the internal comparator cohort ([CDC, 2008](#)) at a significance level of  $\alpha=0.05$ . Calculations were performed using PASS software version 14.

Given that these numbers assume the prevalence of exposure is sufficient to support recruitment of these numbers, the feasibility of achievement will be re-evaluated at each interim review of the data. The interim analysis planned at year 3 after first patient enrolled and annually thereafter ([Section 9.7.1.1](#)), will include sample size re-estimation, examining the observed prevalence and the risk ratio of major congenital malformations

in the erenumab-aooe exposed compared with the internal comparator, accounting for patient recruitment rates and enrollment projections.

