• Study Sample Size

To adequately power an internal comparison of the proportion of major congenital malformation events in the erenumab-aooe exposed, and assuming a 15% drop-out rate and a live birth rate of 62% (FDA, 2002), 1421 erenumab-aooe exposed pregnant women with migraine would need to be enrolled to observe 749 live births. This sample size would provide 80% power to detect a risk ratio of 2.0 or greater in major congenital malformations relative to an assumed prevalence of 3% in the internal comparator cohort (CDC, 2008) at a significance level of  $\alpha=0.05$ .

• Data Analysis

The primary outcome of interest for this study is major congenital malformations; other outcomes are classified as secondary. The overall frequency (proportion, 95% confidence interval [CI]) of selected adverse pregnancy outcomes will be calculated, as well as frequencies of specific outcomes, eg, spontaneous abortions, stillbirths, elective or therapeutic terminations, and preterm births. The same will be calculated for selected adverse fetal, neonatal, and infant outcomes at birth and through at least the first year of life of infants (ie, major and minor congenital malformations, small-for gestational age, and postnatal growth and development). The MACDP birth defects classification system will be used to characterize major and minor congenital malformations for this study.

All analyses will be conducted overall (ever exposed during pregnancy) and by earliest trimester of erenumab-aooe exposure. Data analysis for major congenital malformations will be based on first trimester exposure to erenumab-aooe. The primary data analysis will exclude women who have received first trimester prenatal screening in which either aneuploid disorders or genetic disorders that cause major congenital malformations have been detected, because these disorders are unrelated to medication use. If sufficient numbers are obtained, analyses will also be

presented by the subgroups of maternal age, race/ethnicity, prior history of elective or therapeutic pregnancy termination status, prenatal screening result (positive versus negative), exposure to migraine medications of special interest at baseline, and other important risk factors. Prevalence of primary and important secondary outcome measures and associated 95% CIs will be calculated by subgroups.

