#### 9.2.1.1.1 Metropolitan Atlanta Congenital Defects Program (MACDP)

The MACDP, a population-based tracking system for birth defects, was established in 1967 as the first population-based system for the active collection of information about birth defects in the U.S. (MACDP, 2016). Currently, the MACDP tracking system captures approximately 35,000 births per year from 3 large metropolitan counties in the Atlanta area (5 counties were captured in earlier years). MACDP has monitored trends in birth defects rates and has served as a case registry for descriptive, risk factor, and prognostic studies of birth defects. Since 1998, MACDP surveillance has required that any signs or symptoms of a defect in the child be reported before their sixth birthday. In a 2007 report, the MACDP presented data on the prevalence and descriptive characteristics of birth defects, including 67 individual defects, in metropolitan Atlanta, Georgia, from 1968 to 2003 (Correa et al, 2007).

The frequency of birth defects is measured as prevalence at birth, expressed as the number of affected infants per 1,000 live births. Major structural or genetic birth defects affected approximately 3% of births in the U.S. (CDC, 2008). The prevalence estimates of stillbirth in 2006 and 2008 using MACDP data were 8.0 and 7.6 per 1000 live births plus stillbirths (95% CIs: 7.3, 8.7, and 6.9, 8.4), respectively (Duke and Gilboa, 2014).

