#### **9.7.1.2 Primary Analysis**

The final primary analysis will be conducted once all data collection is complete, including up to 21 months of follow-up for enrolled patients. Annual reports for safety reporting requirements will be generated, with an interim analysis at 3 years.

The primary outcome for this study is the comparison between proportions of major congenital malformations in infants of women with migraine exposed to erenumab-aooe during pregnancy with the unexposed internal comparator. All other outcomes will be classified as secondary. Variables identified for the subgroup analysis will be evaluated as potential confounders in the primary comparative analysis of the risk ratio for major congenital malformations in the erenumab-aooe exposed and unexposed internal comparator.

Data analysis for major congenital malformations will be based on the first trimester exposure to erenumab-aooe. Adjudicated major congenital malformations reported up to 1 year of age by the mother or by an HCP will be included in the primary analysis. Women who have received any first trimester prenatal testing after enrollment, with either negative or positive test result will be included in the primary analysis, **except**:

- Women who have received first trimester prenatal screening, in which either aneuploid disorders or genetic disorders that cause major congenital malformations have been detected, because these disorders are unrelated to medication use
- Any prematurity-related disorders and transient conditions
- Women where the outcome is known, prior to enrollment in the registry, either positive or negative, for major congenital malformations that are unrelated to genetic or aneuploid disorders will be analyzed separately as a subgroup analysis.

In addition to the comparison to an unexposed internal comparator cohort, results will be descriptively compared to existing data sources or published reports representing the general population prevalence of birth defects in the general population (see [Section 9.2.1.1.1](#)). Additional external data sources for comparison will be considered as they become available during the study.

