#### **9.7.2.6 Sensitivity Analysis**

Sensitivity analyses will be performed on both the erenumab-aooe exposed and internal comparator cohorts if sufficient sample size allows, and include but are not limited to the following:

- A sensitivity analysis of major congenital malformations will include women who have received any prenatal screening, regardless of the findings.
- A sensitivity analysis of major congenital malformations will include women where the result is known, regardless of the findings, prior to enrollment in the registry. Subsequently, a sensitivity analysis of major congenital malformations will include women who received any first trimester prenatal screening before enrollment where the result is known to be negative (see [Table 2](#)).
- Sensitivity analyses will also be conducted to study the effects of the timing of erenumab-aooe exposure before and during pregnancy and cumulative exposure periods on each outcome.
- A sensitivity analysis of major and minor congenital malformations will be performed that analyzes different cut points of exposure to erenumab-aooe, accounting for each trimester of exposure. While the primary cut point will be the date of LMP to the end of the first trimester (14 weeks gestation), additional sensitivity cut points will include: 16 weeks prior to LMP through the end of the first trimester, LMP date to the end of pregnancy, 16 weeks prior to LMP to the end of pregnancy, second trimester exposure only, and third trimester exposure only.
- Spontaneous abortions defined as occurring before 22 weeks gestation will also be examined in a sensitivity analysis to account for global variation in the definition for this outcome.
- A sensitivity analysis will be performed to examine the impact of time-varying exposure on primary and secondary outcomes. A time-varying exposure cox regression model will adjust for fixed covariates such as maternal age, presence of comorbidities, previous history of obstetric complications, and gestational age at exposure as time varying covariate. Details will be provided in the SAP.
- For spontaneous abortion, a sensitivity analysis will be performed based on gestational age at enrollment.

Sensitivity analyses may rely on sufficient sample sizes in order to execute. Full details will be described in the SAP.

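### The 80% power claim is calculated for all exposed live births at a 3% rate that includes genetic defects, not for the first-trimester-exposed set that the primary analysis uses

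*Protocol*

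**What the plan says.** **Sample size.** Section 9.5 says that "1421 erenumab-aooe exposed pregnant women with migraine would need to be enrolled to observe 749 live births", after 15% drop-out and a 62% live birth rate. Groups are "1:1 exposed vs. unexposed internal comparator", and the effect is set "relative to an assumed prevalence of 3% in the internal comparator cohort". The Abstract repeats that "This sample size would provide 80% power to detect a risk ratio of 2.0 or greater in major congenital malformations". The Abstract (Data Analysis) and Section 9.1 also call the primary comparison adequately powered.

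**Who counts towards 1421.** The Abstract, Section 9.1 and Section 9.3.1 admit women exposed from 16 weeks before LMP or at any time in pregnancy. Sections 9.2.1 and 9.2.4.1 give 3 months instead of 16 weeks.

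**What the primary analysis uses.** Section 9.7.1.2: "Data analysis for major congenital malformations will be based on the first trimester exposure to erenumab-aooe". Section 9.7.2.6 fixes the window: "While the primary cut point will be the date of LMP to the end of the first trimester (14 weeks gestation". Windows that add the 16 weeks before LMP or the later trimesters are listed there as sensitivity cut points.

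**What the 3% covers.** Section 9.5 cites CDC 2008. Section 9.2.1.1.1 describes the figure from that source: "Major structural or genetic birth defects affected approximately 3% of births in the U.S".

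**What is removed.** The Abstract and Sections 9.7.1.2 and 9.7.2.1 exclude women whose first-trimester screening detected an aneuploid disorder or a malformation-causing genetic disorder. Table 2 is broader: it also removes such disorders among women with no screening before enrollment, and does not limit the exclusion to first-trimester screening.

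**The concern.** A power statement should describe the comparison that will be made. Here the number of exposed births and the background rate both come from a wider set than the primary analysis. Women exposed only before LMP, or only after the first trimester, help to fill the 1421 but are not in the primary exposed group. Some malformations counted in the 3% are taken out of the outcome.

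Two things are at stake. Enrollment could be declared complete at 1421 women while the analysed exposed group is smaller than the calculation assumed. And a null result could be read as having had an 80% chance of detecting a doubling of risk when the chance was lower. The study answers an FDA requirement, so that reading matters.

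**Working it through.** **1. Reproduce the plan's figures.** Inputs from Section 9.5: p0 = 0.03, p1 = 2 × 0.03 = 0.06, alpha 0.05, power 80%, allocation 1:1. The number of sides is not stated. Two-sided reproduces 749, while one-sided gives 590.

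Pooled-variance formula, with p̄ = (p0 + p1)/2 = 0.045:

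n = [1.96·√(2·p̄(1−p̄)) + 0.842·√(p0(1−p0) + p1(1−p1))]² / (p1−p0)² = 748.4, rounded up to **749**.

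Enrollment: 749 / (0.85 × 0.62) = **1421.3**. The other live-birth figures in Table 4 also reproduce (2518 against the stated 2517 for a risk ratio of 1.5, the rest exactly).

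**2. Slack.** Power at 749 per group is 80.03%, and at 748 it is 79.98%. The only two inflation factors are 0.85 and 0.62. There is no factor for the share of exposed births with first-trimester exposure.

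**3. Apply the primary exposure window.** Let f be the share of exposed live births with exposure between LMP and 14 weeks. The protocol does not give f, so the values below are assumptions. The comparator has no exposure window and stays at n0 = 749, and n1 = 749·f.

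Power = Φ{[(p1−p0) − 1.96·s0] / s1}, where s0 = √[p̄(1−p̄)(1/n0 + 1/n1)] with p̄ weighted by group size, and s1 = √[p0(1−p0)/n0 + p1(1−p1)/n1].

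Example, f = 0.8: n1 = 599.2, p̄ = 0.0433, s0 = 0.01116, s1 = 0.01153, so (0.03 − 1.96 × 0.01116)/0.01153 = 0.705 and Φ = 0.760.

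**4. Vary the background rate.** The protocol does not say how much of the 3% is genetic or aneuploid, so 2.7% is an assumption. 3.36% is the birth-defect figure that Section 7.2 quotes for women with migraine. That figure is not stated to exclude genetic cases.

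Power at a true risk ratio of 2.0:

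| First-trimester share f | Rate 2.7% | Rate 3.0% | Rate 3.36% |
|---|---|---|---|
| 1.0 | 76% | 80% | 84% |
| 0.9 | 74% | 78% | 83% |
| 0.8 | 71% | 76% | 81% |
| 0.7 | 69% | 73% | 78% |
| 0.5 | 62% | 66% | 71% |

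At 3%, the risk ratio detectable with 80% power is 2.03, 2.06, 2.11 and 2.24 for f = 0.9, 0.8, 0.7 and 0.5. At 2.7% and f = 0.8 it is 2.14.

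**5. The denominator.** Section 9.7.2.4 defines a total prevalence, which counts cases in live births, fetal deaths and terminations over pregnancies other than spontaneous losses and ectopic or molar pregnancies. It also defines a prevalence at birth, and does not say which is primary. Of 1421 × 0.85 = 1208 retained pregnancies, about 1208 − 749 = 459 are not live births. How these divide between spontaneous losses and other outcomes is not given. If, as an assumption, 101 of them entered each arm's denominator (850 per arm before the window is applied), power at f = 0.8 and 3% would be 81%. With 151 (900 per arm) it would be 83%.

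**The case against.** Several parts of the defence stand.

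- **The arithmetic is right.** A reader might infer a calculation error. There is none. The fault is an unstated assumption that every exposed birth is first-trimester exposed and that the outcome rate is the full 3%.
- **The loss may be small or nil.** A reader might infer that power is certainly below 80%. The documents do not show that. At a 90% share and 3%, power is 78%, which is minor. A rate above 3% or the total-prevalence denominator could restore about 81% at an 80% share. Section 7.2 also quotes 4.2% from a triptan registry.
- **Unplanned pregnancies do not prove a large loss.** Section 7.2 says that almost half of pregnancies are unplanned. That does not show that many women stop before LMP. Unplanned pregnancy on a preventive drug makes exposure after LMP more likely.
- **The other exclusions do not prove a lower rate.** Section 9.7.2.1 also removes prematurity-related and transient conditions, but nothing shows that the 3% includes them. Section 9.3.2.1.1 notes that the classification already omits some conditions altogether. Likewise, how far the genetic exclusion lowers the rate depends on whether Section 9.7.1.2 or Table 2 governs.
- **There is partial mitigation.** Section 9.5 promises sample size re-estimation from year 3 using observed prevalence and risk ratio, which could detect a low background rate. Section 9.7.1.1 has the interim report summarise exposure classification. Section 7.3 frames the primary objective as a risk ratio with a 95% confidence interval, which would show lost precision.

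These points limit the size of the concern but do not remove it. No passage sets or tracks a number of first-trimester-exposed births. Section 9.9.3 warns about low enrollment, whereas this mismatch arises even if all 1421 women enroll. The possible offsets are not part of the protocol's calculation, so they cannot support its claim.

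**Conclusion.** The concern holds in a limited form. The 749, 1421 and 80% are computed correctly for all exposed live births at a 3% rate that includes genetic defects. They are not computed for the primary analysis, and the calculation has no margin for the difference. The unconditional power claim in the Abstract, Section 9.1 and Section 9.5 is therefore unsupported for the comparison it describes.

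The size rests on two inputs that the protocol does not give: the first-trimester share and the background rate after the genetic exclusion. At 3%, shares from 90% down to 50% give 78% down to 66%. Adding a 2.7% rate at an 80% share gives 71%. A background rate above 3%, or the wider denominator, pushes the other way. What can be said firmly is that the claim is conditional on assumptions nobody has stated.

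**What to change.** Keep 1421 as the enrollment figure and change the wording and the calculation around it.

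1. In the Abstract, Section 9.1, Section 9.5 and Table 4, state that 749 is all exposed live births.
2. In Section 9.7.2.4, name which prevalence and denominator is primary.
3. Reconcile Table 2 with Sections 9.7.1.2 and 9.7.2.1 on which genetic and aneuploid cases are excluded.
4. Replace the unconditional power statement with power, or detectable risk ratio, for the first-trimester-exposed primary set. Cover a stated range of first-trimester share and of background rate, both below and above 3%.
5. At each interim re-estimation, report the count of first-trimester-exposed births eligible for the primary analysis.

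The cost is a re-run calculation and text changes, and the stated power is likely to become less favourable. This does not ask for 749 births inside the primary set. At 3% that would need 1421.3/0.8 = 1777 exposed women at an 80% share, or 1421.3/0.5 = 2843 at 50%, so it could not be had without more patients. Changing the primary exposure window is a separate design choice and is not needed here.
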